7.2. Selection of Study Population

7.2.1. Number of Patients

Approximately 160 patients will be enrolled: approximately 60 patients enrolled in Cohort 1, approximately 30 patients enrolled in Cohort 2, approximately 30 patients will be enrolled in Cohort 3, approximately 10-12 patients will be enrolled in Cohort 4, and approximately 30 patients will be enrolled in Cohort 5. Cohorts 2 and 3 enrolled patients in parallel.

7.2.2. Subject Eligibility

7.2.2.1. Inclusion Criteria

Patients may be included in the study only if they meet all of the following inclusion criteria at the time of study enrollment:

1. Read, understood, and provided written informed consent and, if applicable, Health Insurance Portability and Accountability Act (HIPAA) authorization after the nature of the study has been fully explained and must be willing to comply with all study requirements and procedures.
2. Advanced (unresectable Stage III or Stage IV) histologically-confirmed melanoma.
3. Documented progressive disease, based on radiographic, clinical or pathologic assessment, during or subsequent to the last anticancer therapy. For Cohorts 3 and 5, progression (confirmed from two scans at least 4 weeks apart) must have occurred during the PD-1 targeted CPI treatment and the investigator has deemed it appropriate to continue to treat beyond confirmed disease progression.
4. No more than 1 prior chemotherapy-containing regimen for advanced disease. For Cohorts 1, 2, and 4, prior treatments received must include at least one check-point inhibitor (e.g., anti-CTLA-4-, PD-1-, PD-L1-targeted immunotherapy) and for patients with a BRAF mutation, at least one BRAF- or MEK-targeted therapy, unless patients are not candidates for, or refused, these therapies. For Cohorts 3 and 5, prior treatment received must include a PD-1 targeted CPI (i.e., nivolumab or pembrolizumab) administered during the most recent disease progression and for patients with a BRAF mutation, at least one BRAF- or MEK-targeted therapy when appropriate.
5. Pre-treatment tumor tissue, and for Cohorts 2 and 3 a skin biopsy, available for retrospective evaluation of gpNMB in tumor or normal epithelial cells, respectively, by central immunohistochemistry (IHC):
 - a. All patients in Cohorts 1-3 must submit an archival FFPE tumor tissue sample representative of advanced (Stage III or IV) disease, obtained more than 12 weeks prior to study entry (Historic sample).
 - b. All patients in Cohorts 1-3 are also required to submit a second, recently-obtained FFPE tumor tissue sample (Pre-entry sample). Tissue should be obtained within the 12 weeks prior to study entry, be subsequent to the last systemic anticancer therapy received, and be post-tumor progression.
 - c. All patients in Cohorts 4-5 are required to submit a fresh Pre-entry tumor tissue sample

as well as a fresh On-treatment tumor tissue sample. Pre-entry tissue should be obtained within the 12 weeks prior to study entry, be subsequent to the last systemic anticancer therapy received, and be post-tumor progression. Tumor tissue samples will be collected until such time Celldex informs the sites that further data is not needed.

For patients who need to undergo a new biopsy to obtain a Pre-entry, or both Pre-entry and On-treatment, sample, biopsy sites must be soft tissue or visceral tumor lesions that can be biopsied with acceptable clinical risk (as judged by the investigator). The biopsy site chosen should have not been previously irradiated. Biopsy sites must be distinct from RECIST 1.1 target lesions, unless, in the case of the Pre-entry biopsy, the biopsy is obtained more than 10 days prior to the Screening Disease Assessment. Patients must be separately consented for collection of a fresh Pre-entry, or both Pre-entry and On-treatment sample.

- d. All patients in Cohorts 2 and 3 must agree to submit a recently-obtained FFPE skin fold (axilla or groin) biopsy (Pre-entry sample). Tissue may be obtained by punch biopsy or surgical excision. Skinfold biopsies will be collected until such time Celldex informs the sites that further data is not needed.

NOTE: Patients who cannot fulfill the requirement for either the Historic, Pre-entry, or On-treatment sample submission in Cohorts 1-5 may be enrolled in the study with prior permission of the Celldex Medical Monitor. In no case will a patient be allowed to enter the study without at least one available tumor sample.

6. Male or female patient ≥ 18 years of age
7. Eastern Cooperative Oncology Group (ECOG) Performance Status 0 to 1 ([Appendix 4](#))
8. Life expectancy of ≥ 12 weeks
9. Measurable (target) disease by RECIST 1.1 criteria ([Eisenhauer, Therasse et al. 2009](#)) ([Appendix 3](#)). Target lesions selected for tumor measurements should be those where additional (e.g., palliative) treatments are not indicated or anticipated.
10. Resolution of toxicities related to prior therapies (including radiotherapy) to \leq NCI-CTCAE Grade 1 severity, except for alopecia, grade 2 fatigue, vitiligo, or endocrinopathies on replacement therapy
11. Screening laboratory values must meet the following criteria:
 - Absolute neutrophil count (ANC) $\geq 1500/\text{mm}^3$
 - Hemoglobin ≥ 9.0 g/dL
 - Platelet count $\geq 100,000/\text{mm}^3$
 - Calculated creatinine clearance > 40 mL/min per the Cockcroft and Gault formula ([Appendix 5](#)) or Serum Creatinine ≤ 2.0 mg/dL
 - Alanine transaminase (ALT) ≤ 3.0 x upper limit of normal (ULN) (≤ 5.0 x ULN in the case of liver metastases)
 - Aspartate transaminase (AST) ≤ 3.0 x ULN (≤ 5.0 x ULN in the case of liver metastases)

- Total bilirubin $\leq 1.5 \times \text{ULN}$ ($\leq 5.0 \times \text{ULN}$ in the case of liver metastases). Patients with known Gilbert's syndrome may be enrolled with total bilirubin $\leq 3.0 \text{ mg/dL}$
12. Both men and women enrolled in this trial must use effective contraception during the course of the trial and for at least two months after discontinuing study treatment. Effective contraception is defined as double barrier contraception (e.g., condom plus spermicide in combination with a female condom, diaphragm, cervical cap, contraceptive sponge or vaginal ring), intra-uterine device (IUD), implants, injectables, combined oral contraceptives, sexual abstinence (total abstinence from sexual intercourse as the preferred lifestyle of the patient; periodic abstinence is not acceptable), or sexual intercourse with only a vasectomized partner. Patients and/or partners who are surgically sterile or postmenopausal are exempt from this requirement.

7.2.2.2. Exclusion Criteria

Patients will be excluded from the study for any of the following reasons:

1. Received glembatumumab vedotin (CR011-vcMMAE; CDX-011) or other MMAE-containing agents previously
2. BRAF/MEK inhibitors within 2 weeks prior to the first dose of study treatment.
3. Use of any monoclonal based therapies within 4 weeks, except for the PD-1 targeted CPI (i.e., nivolumab or pembrolizumab) in Cohort 3, and all other immunotherapy (tumor vaccine, cytokine, or growth factor given to control the cancer) within 2 weeks, prior to the first dose of study treatment.
4. Chemotherapy within 21 days or at least 5 half-lives (whichever is longer) prior to the planned start of study treatment
5. [criterion deleted]
6. Major surgery within 4 weeks prior to the first dose of study treatment. Surgery requiring local/epidural anesthesia must be completed at least 72 hours before study drug administration and patients should be recovered.
7. Use of other investigational drugs within 2 weeks or 5 half-lives (whichever is longer) prior to study treatment administration
8. Patients with ocular melanoma
9. Neuropathy > NCI-CTCAE Grade 1
10. Subjects with a history of allergic reactions attributed to compounds of similar composition to dolastatin or auristatin. Compounds of similar composition include Auristatin PHE as an anti-fungal agent, Auristatin PE (TZT-1027, Soblidotin, NSC-654663) as an anti-tumor agent and symprostatin 1 as an anti-tumor agent.
11. Active, untreated central nervous system metastases, except for patients with ≤ 3 small ($< 0.6 \text{ cm}$) asymptomatic lesions where treatment is not indicated. Patients with brain metastases identified at Screening may be rescreened after the lesion(s) have been appropriately treated; patients with treated brain metastases should be neurologically stable for 4 weeks post-treatment and prior to study enrollment, and off corticosteroids for at least 2 weeks before administration of study drugs.

12. Women who are pregnant or lactating. All female patients with reproductive potential must have a negative pregnancy test prior to starting treatment.
13. History of alternate malignancy except for adequately treated and cured basal or squamous cell skin cancer, curatively treated *in situ* disease, or any other cancer from which the patient has been disease-free for ≥ 3 years
14. Significant cardiovascular disease including unstable angina pectoris, uncontrolled hypertension or arrhythmia, congestive heart failure (New York Heart Association Class III or IV) related to primary cardiac disease, ischemic or severe valvular heart disease or a myocardial infarction within 6 months prior to the first dose of study treatment
15. Known alcohol or drug abuse
16. Known infection with Human Immunodeficiency Virus (HIV), Hepatitis B (HBV) or Hepatitis C (HCV)
17. Any underlying medical condition that, in the investigator's opinion, will make the administration of glembatumumab vedotin hazardous to the patient, or would obscure the interpretation of toxicity determination or adverse events

Additional Exclusion Criteria for Cohort 2 Only

In addition to the exclusion criteria above, patients will be excluded from Cohort 2 for the following reason:

18. Previous treatment with varlilumab or any other anti-CD27 mAb

Additional Exclusion Criteria for Cohorts 2-5

In addition to the exclusion criteria above, patients will be excluded from Cohorts 2-5 for the following reasons:

19. Active systemic infection requiring treatment. Infection controlled by oral therapy will not be exclusionary. Note: microscopic examination of urinalysis is required during screening. If urinary infection is suspected, then a negative urine culture is required prior to enrollment.
20. Use of immunosuppressive medications within 4 weeks or systemic corticosteroids within 2 weeks prior to first dose of study treatment. Topical, inhaled or intranasal corticosteroids (with minimal systemic absorption) may be continued if the patient is on a stable dose. Non-absorbed intraarticular corticosteroid and replacement steroids (≤ 10 mg/day prednisone or equivalent) will be permitted.
21. Active autoimmune disease or a documented history of autoimmune disease, or history of potential autoimmune syndrome that required systemic steroids or immunosuppressive medications, except for patients with vitiligo, endocrinopathies, type 1 diabetes, or patients with resolved childhood asthma/atopy or other syndromes which would not be expected to recur in the absence of an external trigger (e.g., drug-related serum sickness or post-streptococcal glomerulonephritis). Subjects with mild asthma who require intermittent use of bronchodilators (such as albuterol) who have not been hospitalized for asthma in the preceding 3 years will not be excluded from this study.

Additional Exclusion Criteria for Cohorts 3 and 5 Only

In addition to the exclusion criteria above, patients will be excluded from Cohorts 3 and 5 for the following reasons:

22. Interstitial lung disease that is symptomatic or may interfere with the detection or management of suspected drug-related pulmonary toxicity
23. Active diverticulitis

Additional Exclusion Criteria for Cohorts 4 and 5 Only

In addition to the exclusion criteria above, patients will be excluded from Cohorts 4 and 5 for the following reasons:

24. Any non-study vaccination within 4 weeks, or influenza vaccine within 2 weeks, prior to CDX-301 dosing

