
Study Treatment Dosing and Administration
	
Glembatumumab vedotin will be administered on Day 1 of repeated 21 day cycles in Cohorts 1-5. The starting glembatumumab vedotin dose is 1.9 mg/kg, given as a 90-minute intravenous infusion using a 0.22 micron in-line filter. Treatment will continue until progression or intolerance.
 
In Cohort 2, varlilumab will be administered on Day 1 of Cycles 1, 2, 4, 6, 8, and 10 for a total of up to 6 doses. The dose of varlilumab will be 3.0 mg/kg (or 0.3 mg/kg in the event of treatment-limiting toxicity as described above), administered as a 90-minute intravenous infusion using a volumetric pump with a 0.2 micron pore size, low-protein binding polyethersulfone (PES) membrane in-line filter.
 
In Cohort 2, glembatumumab vedotin and varlilumab will be administered as separate infusions. Varlilumab should be the first infusion and glembatumumab vedotin administered at least 30 minutes after varlilumab infusion. After cycle 10, glembatumumab vedotin treatment as a monotherapy will continue until confirmed progression or intolerance.
 
In Cohort 3, the dose and dosing regimen for the PD-1 targeted CPI will continue per institutional standard of care with reference to the package insert. The first dose of PD-1 targeted CPI may or may not be on the same day of the initiation of glembatumumab vedotin treatment. When both glembatumumab vedotin and the PD-1 targeted CPI are administered on the same day, the drugs will be administered as separate infusions. The PD-1 targeted CPI should be the first infusion and glembatumumab vedotin administered at least 30 minutes later as the second infusion. After initiation of glembatumumab vedotin treatment, CPI will be administered in combination with glembatumumab vedotin until disease progression (using study screening disease assessment as baseline reference) or intolerance.
 
In Cohort 4, two priming cycles of CDX-301 will be administered subcutaneously at a dose of 75 µg/kg for 5 consecutive days (Cycle 1 Days -6 to -2 and Cycle 1 Days 15-19) prior to glembatumumab vedotin on Day 1 in Cycles 1 and 2. Glembatumumab vedotin treatment as a monotherapy will continue to be administered at repeated 21 day cycles until disease progression or intolerance.
 
In Cohort 5, two priming cycles of CDX-301 will be administered subcutaneously at a dose of 75 µg/kg for 5 consecutive days (Cycle 1 Days -6 to -2 and Cycle 1 Days 15-19) prior to glembatumumab vedotin on Day 1 in Cycles 1 and 2. Glembatumumab vedotin

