20. Imaging-based evaluation per RECIST 1.1 should be performed. Contrast-enhanced Computed Tomography (CT) of the chest, abdomen, and pelvis, as well as all other suspected disease sites is required. Magnetic Resonance Imaging (MRI) exams of the brain, abdomen, and pelvis can be performed in lieu of a CT; however, MRI exams of the chest are not recommended. In the event that a chest MRI is performed, a non-contrast chest CT is strongly recommended to evaluate the lung parenchyma. Brain and/or bone scans are required for any patients with a history of metastases to bone and/or brain or where symptomatology raises the suspicion for bone and/or brain metastases. Lesions identified on bone scans should be confirmed by a CT or MRI at baseline, and, if identified as target lesions due to soft tissue component, they should continue to be followed by the same methodology (i.e., CT or MRI scan). However, bone lesions followed as non-target disease may be subsequently followed by bone scans only. Lesions that cannot be imaged but are assessable by clinical exam may be assessed by color photography including a ruler (preferred method) or measured with calipers. Normally, all target and non-target disease sites should be evaluated at each assessment. However, for patients with non-target bone disease, bone scans need only be repeated every twelve to eighteen weeks, or more frequently if clinically indicated. The same method of assessment and the same technique should be used to characterize each identified and reported lesion at baseline and during follow-up. Target lesions selected for tumor measurements should be those where surgical resection or radiation are not indicated or anticipated.
21. Unless otherwise specified, all study assessments should be performed prior to administration of study treatment(s), and may be performed up to 24 hours prior to treatment administration if assessments remain within the specified visit window.
22. The intent is for CDX-301 to be administered for 5 consecutive days on Monday through Friday, followed by glembatumumab vedotin treatment (and PD-1 targeted CPI for Cohort 5) on the following Monday. CDX-301 administration is allowed on weekend days if the site has the ability to do so. Ideally, CDX-301 should be administered at approximately the same time each day. Patients should be observed on Day -6 prior to Cycle 1 for at least 1 hour after CDX-301 injection, and for at least 30 minutes at all subsequent CDX-301 doses.

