23. In Cohort 5, administration of the PD-1 targeted CPI should be continuous from the prior standard of care treatment regimen during which the most recent disease progression occurred. No more than 3 doses of nivolumab or 2 doses of pembrolizumab should be missed between the most recent disease progression and initiation of treatment on study. Day 1 of Cycle 1 occurs with the first dose of glembatumumab vedotin which, in Cohort 5, is administered on the same day as the PD-1 targeted CPI. When both glembatumumab vedotin and the PD-1 targeted CPI are administered on the same day, the drugs will be administered as separate infusions. The PD-1 targeted CPI should be the first infusion and glembatumumab vedotin administered at least 30 minutes later as the second infusion. Patients should be observed on Cycle 1 Day 1 for at least 2 hours after administration of the last study drug, and for at least 1 hour at all subsequent dosing visits. Infusions should be given in a monitored setting that has ready access to an intensive care unit in case of a severe infusion reaction. The PD-1 targeted CPI will be administered in combination with glembatumumab vedotin until disease progression (using study screening disease assessment as baseline reference) or intolerance.
Additional clinic visits and monitoring (such as laboratory assessments) relevant to the administration of the PD-1 targeted CPI will be conducted in accordance with standard of care when appropriate. However, all CPI dosing and adverse events occurring between study visits will be documented in the eCRF.
24. All concomitant medication will be documented in the Case Report Form (CRF) if taken within 28 days prior to Study Day 1, and either (whichever occurs sooner): a) 28 days after last dose of study treatment or b) initiation of alternate anti-cancer therapy. In addition, all anti-cancer medications should be recorded throughout the duration of study follow-up.
25. For patients who develop grade 3 treatment-related rash and who provide appropriate consent, punch biopsies and photographs of the rash, as well as uninvolved skin, are strongly encouraged. Samples may be analyzed centrally; in these cases, collection, processing and shipping instructions will be provided separately.
26. Adverse event monitoring on Cycle 1 Day 7 can be performed in person or by telephone to determine if the patient is experiencing any adverse events.

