8.6.3. PD-1 Targeted Checkpoint Inhibitor

The PD-1 targeted CPI should be administered in accordance with institutional standard practice with reference to the manufacturer's package insert. Dosing of these CPIs should not be omitted or significantly delayed to accommodate other study treatments being administered in this study. In Cohorts 3 and 5, no more than 3 doses of nivolumab or 2 doses of pembrolizumab should be missed prior to initiation of glembatumumab vedotin therapy.

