10.2.2. Safety Variables

10.2.2.1. Adverse Events: Definition

An adverse event is any untoward medical occurrence in a patient administered a study treatment. An adverse event (AE) can therefore be any unfavorable and unintended sign (including an abnormal laboratory finding), symptom, or disease temporally associated with the use of a study treatment, whether or not related to the study treatment. All observed or volunteered adverse events regardless of suspected causal relationship to the study treatment will be reported, as described in the following sections. For the purposes of this current study, “study treatment” is defined as glembatumumab vedotin and/or: varlilumab, nivolumab, pembrolizumab, or CDX-301.

For all adverse events, the investigator is responsible for obtaining information adequate to determine the:

- appropriate descriptive term: Adverse events should be reported using concise medical terminology, preferably referring to the syndrome/diagnosis rather than symptoms, when possible.

- severity of the event: adverse event severity will be primarily assessed using NCI Common Terminology Criteria for Adverse Events v4.0. (NCI-CTCAE), Version 4.0, division of Cancer Treatment and Diagnosis (DCTD), National Cancer Institute ([Robert, Thomas et al.](#)), National Institute of Health (NIH), Department of Health and Human Services (DHHS) published May 29, 2009 at https://ctep.cancer.gov/protocoldevelopment/electronic_applications/ctc.htm
- onset/resolution dates and outcome
- causality: the relationship of each adverse event to study drug will be defined as “unrelated” or “related” to study treatment:
 - Unrelated: There is little or no possibility that the study drug caused the reported adverse event; and other factor(s) including concurrent illnesses, progression and expression of the disease state, concurrent medications, or a reaction to concurrent medications appear to explain the adverse event.
 - Related: there exists at least a reasonable possibility that the study treatments caused or contributed to the adverse event; an inability to identify an alternate etiology for an adverse event should not, by itself, justify a “related” attribution.
- whether it meets the criteria for classification as a serious adverse event (see [Section 10.2.2.2](#))

The following study-specific points of clarification should be noted when considering adverse event reporting and recording:

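### Exclusion 3 waives the 4-week antibody washout for PD-1 inhibitors only in Cohort 3, so at 2- or 3-week dosing it bars Cohort 5 patients on uninterrupted PD-1 therapy

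*Protocol*

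**What the plan says.** Exclusion 3 stands among criteria 1 to 17, which apply to every cohort. It excludes patients who had monoclonal antibody therapy in the 4 weeks before the first dose of study treatment, "except for the PD-1 targeted CPI (i.e., nivolumab or pembrolizumab) in Cohort 3". The synopsis carries the same wording.

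Other sections treat Cohort 5 like Cohort 3:

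- Inclusions 3 and 4 (Section 7.2.2.1) require, for both cohorts, confirmed progression while on nivolumab or pembrolizumab, and an investigator's judgement that treatment beyond progression is appropriate.
- Table 2 footnote 23: "In Cohort 5, administration of the PD-1 targeted CPI should be continuous from the prior standard of care treatment regimen".
- Section 8.6.3: "In Cohorts 3 and 5, no more than 3 doses of nivolumab or 2 doses of pembrolizumab should be missed" before glembatumumab vedotin starts. The same section says the inhibitor should not be skipped or appreciably held back to make room for other study drugs.
- Exclusions 22 and 23 name Cohorts 3 and 5 together.

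On timing, the protocol states no interval for the inhibitor: "The PD-1 targeted CPI should be administered in accordance with institutional standard practice". Cohort 5 patients start CDX-301 on Cycle 1 Day -6, before glembatumumab vedotin on Day 1.

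**The concern.** The reason for exempting Cohort 3 is that its patients stay on their PD-1 inhibitor; the Amendment 3 summary of changes gives this as the rationale. Cohort 5 patients are meant to do the same, yet they are not exempted. Section 10.1.2 allows enrolment only once every exclusion has been ruled out, so the criterion binds. Read literally, it turns away patients who follow the continuity instruction and accepts those with a long enough break in treatment. Holding the inhibitor so that a patient qualifies would go against Section 8.6.3. Sites would have to screen out intended patients or record eligibility deviations, and they might not all choose alike.

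**Working it through.** The plan gives no figure to reproduce. The check is date arithmetic.

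**Inputs from the protocol**

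- Washout window: 4 weeks = 28 days (Exclusion 3).
- First CDX-301 dose to Day 1: footnote 22 of Table 2 says "The intent is for CDX-301 to be administered for 5 consecutive days on Monday through Friday", with glembatumumab vedotin on the following Monday. Day -6 is therefore 7 days before Day 1, or 6 to 10 days with the Table 2 window for Day 1 (+3/-1 days).
- Permitted missed doses: up to 3 of nivolumab or 2 of pembrolizumab.
- Start of the count: Section 10.2.2.1 says study treatment "is defined as glembatumumab vedotin and/or: varlilumab, nivolumab, pembrolizumab, or CDX-301". This supports counting to CDX-301 on Day -6; Day 1 is shown as the alternative.

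**Assumptions**

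- Inhibitor interval *I* of 2, 3, 4 or 6 weeks (none is stated).
- The next on-schedule inhibitor dose falls on Cycle 1 Day 1. Footnote 23 puts it on the same day as glembatumumab vedotin.

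**Formulas**, with *m* missed doses:

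- Last inhibitor dose to Day 1 = 7 × *I* × (*m* + 1) days.
- Last inhibitor dose to Day -6 = that figure minus 7 (range: minus 10 to minus 6).

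**Uninterrupted therapy (*m* = 0)**

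| Interval | To Day 1 | Result | To Day -6 (range) | Result |
|---|---|---|---|---|
| 2 weeks | 7×2×1 = 14 | excluded | 14−7 = 7 (4–8) | excluded |
| 3 weeks | 7×3×1 = 21 | excluded | 21−7 = 14 (11–15) | excluded |
| 4 weeks | 7×4×1 = 28 | boundary | 28−7 = 21 (18–22) | excluded |
| 6 weeks | 7×6×1 = 42 | clears | 42−7 = 35 (32–36) | clears |

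**With missed doses**

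| Interval | Missed | To Day 1 | Result | To Day -6 (range) | Result |
|---|---|---|---|---|---|
| 2 weeks | 1 | 7×2×2 = 28 | boundary | 21 (18–22) | excluded |
| 2 weeks | 2 | 7×2×3 = 42 | clears | 35 (32–36) | clears |
| 3 weeks | 1 | 7×3×2 = 42 | clears | 35 (32–36) | clears |
| 4 weeks | 1 | 7×4×2 = 56 | clears | 49 (46–50) | clears |

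The continuity rule and Exclusion 3 are therefore not mutually exclusive: a long enough permitted gap satisfies both. Not every permitted gap is long enough, and at 2 or 3 weeks no gap at all fails on either count. The Day 1 visit window changes none of the Day -6 results.

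**The case against.** The strongest reply is that this is an incomplete update with little reach. Amendment 3 added the exemption, Amendment 4 added Cohort 5, and Section 7.1 says Cohort 5 patients continue their inhibitor in the same way as Cohort 3, so the intent is plain. Enrolment follows sponsor instructions, so a query or a deviation note is likelier than silent misapplication. Only some patients are caught. Take nivolumab every 2 weeks with 0 to 3 missed doses and pembrolizumab every 3 weeks with 0 to 2. Counted to Day -6, 4 of these 7 permitted schedules clear the window (2 and 3 missed; 1 and 2 missed). No endpoint, test or sample size changes. Sections 5 and 8.5 are also redacted in the public text.

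Most of this stands as a limit on consequence. An omission when Cohort 5 was added is the likeliest cause, though that is an inference. The 4 of 7 counts schedules, not patients, and the documents give no frequencies. The redactions mean one can say only that no visible text extends the exemption. But clear intent elsewhere does not alter a criterion that Section 10.1.2 makes a condition of entry. The eligibility section gives the medical monitor explicit discretion over missing tumour samples, not over the antibody washout.

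**Conclusion.** The concern holds. On the visible text, Exclusion 3 shuts out Cohort 5 patients on uninterrupted PD-1 therapy at an assumed 2- or 3-week interval, whichever dose starts the clock. At 4 weeks they are excluded counting to Day -6 and on the boundary counting to Day 1; at 6 weeks they clear.

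The criterion would apply to about 30 patients if Cohort 5 opens. No number excluded and no shift in the enrolled population can be claimed, because the share on uninterrupted therapy is unknown. The SAP covers Cohorts 1 to 3 only, so none of its analyses is affected. The error makes entry stricter and adds no safety risk. It should be corrected before Cohort 5 enrols.

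**What to change.** In Exclusion 3, change the exemption from Cohort 3 to Cohorts 3 and 5, in both the synopsis and Section 7.2.2.2. The inhibitor then no longer triggers the exclusion in Cohort 5 at any interval or gap, and the missed-dose limit in Section 8.6.3 governs, as it does for Cohort 3. The cost is two wording changes in a protocol amendment, with no extra patients, procedures or analyses and no change to sample size or power.
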